1.5 Sample Size Justification

We expect to enroll 510 mother, father and child triads in 104 villages (clusters) in the Thies, Diourbel and Fatick regions of Senegal as part of this study. We plan to include ~5 triads per village. Our sample size estimation was calculated based on our two primary outcomes: the prevalence of MAD and anemia.

The sample size estimate is informed by our prior cross-sectional research on over 1200 household surveys and our pilot data over a 4-week intervention period (unpublished data).² Attrition was 2%, anemia prevalence was 66% and MAD prevalence was 46.8%. Assuming a conservative intra-class correlation coefficient of 0.02,³ 5% attrition (based on our pilot work and previously published community-based research projects in Senegal),^{29,30} and a 2-sided significance level of 0.05, 102 clusters with 5 triads per cluster will provide 81.7% power to detect a 6% absolute difference in anemia and 88.8% power to detect an absolute difference of

7% in MAD. Our pilot study found a 19.2% increase in MAD. Even if we assume 10% attrition, we will still have 80% power to detect a 6% absolute difference in anemia and 87.3% power to detect an absolute difference of 7% in MAD. Improvements in anemia and MAD prevalence of 6% and 7%, respectively are clinically relevant and aligned with improvements in previously published studies.^{31,32}

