cRCT sample. The villages in which we are conducting this study are subsistence farming communities with high levels of poverty and malnutrition in three regions of Senegal: Thies, Diourbel and Fatick. Each of the 104 villages that will be included in the study have been purposively selected to ensure that they have an established farming group, and that they are sufficiently geographically dispersed in order to minimize risk of contamination. We will use the list of the household members of the farming groups of each of the 104 villages included in the cRCT as our sampling frame. Based on [name] previous experience, we will identify all households within the farming group that have a child 6-19 months of age at baseline (to ensure that the child is not >23 months at endline), and we will subsequently randomly select five mother, father and child triads to be included in our study sample. In some cases, the primary caregiver of the child may be a close relative rather than the birth mother. In these instances, the primary caregiver will receive the voice and text messages along with her husband or primary male caregiver. In total, we will sample 510 triads in 104 villages (~5 households/triads per village). Thus, our sample will include 510 mother, father and child triads. Baseline data collection will take place in May/Jun 2022, the intervention will be delivered between Jun-Sep 2022 and the endline data collection will take place in October 2022.

Process Evaluation sample: A smaller purposive sample of approximately 45 mothers and fathers, implementation project staff and CHWs will be included in Aim 2 of the project as part of the in-depth semi-structured interviews and focus groups conducted in the process evaluation. We will purposively select three villages from each region (n total = 9 villages) in order to maximize variation in village characteristics such as size, distance to urban settings, distance to markets, etc. Interviewees and focus group participants will be purposively selected from the list of all mothers and fathers receiving the voice messages in each of these villages to ensure variation in participant socio-demographics (e.g., household size, parity, age, etc.) as well as key people involved in the intervention's implementation. The process evaluation data collection will take place in between October and December 2022.

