1.4 Preliminary Data

We previously conducted a pilot of a modified version of this intervention. In our pilot research, we conducted focus groups (n=6) with mothers and fathers of young children, and completed a comprehensive survey of ~1200 households in Senegal, to identify key IYCF practices to target. We then developed 8 voice messages (based on the theory of planned behavior (TPB)²⁰) targeting the identified IYCF practices and conducted a pre- and post-intervention pilot study to examine its feasibility and potential for impact with a small sample of mother, father and child (6-23 months of age) triads (n=47).²¹ After the intervention, we found an improvement in the consumption of nutrient-rich foods and a greater proportion of children consuming a minimum acceptable diet (MAD) (19% higher in intervention as compared to the control group),²¹ an indicator of dietary diversity that is associated with nutrient adequacy, reduced stunting and underweight in children.²² However, we were limited by a small sample size and a lack of control group, which this study is designed to overcome.

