1.6 Study Variables

A. Independent Variables, Interventions, or Predictor Variables

An mHealth messaging intervention will be delivered to the intervention group for this study, as described above. The intervention will be 16 weeks in duration and include both scripted and unscripted messages related to 8 key IYCF behaviors.

B. Dependent Variables or Outcome Measures

Table 1 provides an overview of our primary and secondary study outcomes.

Table 1. Study outcomes

Outcome type	Outcome	Description
Primary	Anemia prevalence	We will use Hemocue Hb301 machines to measure hemoglobin levels in children in order to determine anemia prevalence using the WHO cut-offs: mild $10 \leq \text{hb} < 11 \text{ g/dl}$; moderate $7 \leq \text{hb} < 10 \text{ g/dl}$ and severe $\text{hb} < 7 \text{ g/dl}$. A finger prick will be used to obtain a drop of capillary blood that is placed on a cuvette and inserted in the Hemocue machine to obtain an on-the-spot assessment of hemoglobin levels.
	Minimum Acceptable Diet	Minimum Acceptable Diet Prevalence, Primary, baseline and endline: The minimum acceptable diet indicator will be used to assess dietary diversity in children. A 24-hour open dietary recall will be conducted with mothers to assess their child's dietary intake over the previous day. The 24-hour recall will be used to calculate minimum dietary diversity (MDD) (consuming ≥ 4 of 7 food groups (grains, roots and tubers; legumes and nuts; dairy products; flesh foods; eggs; vitamin A rich fruits and vegetables; other fruit and vegetables)) and minimum meal frequency (MMF) (2x/day for breastfed infants 6-8.9 months; 3x/day for breastfed children 9-23.9 months; 4x/day for non-breastfed children 6-23.9 months). Children who meet the thresholds for both MDD and MMF are defined as consuming a MAD, based on the WHO/UNICEF IYCF indicator.

Secondary	Frequency of consuming key foods in past 7 days	Frequency of consuming key foods in the past 7 days, Secondary, baseline and endline: We will use a 7-day food frequency questionnaire (FFQ) to assess the frequency that children consumed specific foods targeted in the intervention over the course of the previous week. More specifically, the FFQ will ascertain the number of times that the following foods have been consumed: eggs, leafy greens, fish, milk, cowpea, nuts, orange colored fruits and vegetables, other fruits and vegetables, thick porridge, beef or mutton, pork, chicken and liver.

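### The power stated in Protocol 1.5 (81.7% anemia, 88.8% MAD) does not follow from its listed inputs; it needs an unstated within-child correlation of about 0.89

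*Protocol*

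**What the plan says.** Protocol 1.5 bases the sample size on two primary outcomes, anemia and MAD prevalence. It takes its inputs from a cross-sectional survey and a 4-week pilot: "Attrition was 2%, anemia prevalence was 66% and MAD prevalence was 46.8" per cent. It adds an intra-cluster correlation (ICC) of 0.02, 5% attrition and a two-sided 0.05 level, and concludes that "102 clusters with 5 triads per cluster will provide 81.7% power to detect a 6% absolute difference in anemia and 88.8% power" for 7 points in MAD. A sensitivity statement follows: "Even if we assume 10% attrition, we will still have 80% power to detect a 6% absolute difference in anemia and 87.3% power" for the same MAD difference. Section 4.3 C repeats that power is adequate for both targets even at 10% attrition.

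Section 1.3 allocates villages 1:1, and section 1.9 has each household visited at baseline and at endline. Protocol 6.1 and the SAP's description of the statistical approach fit a difference-in-differences model whose intervention-by-time interaction is the estimate of interest. No power formula is named and no baseline-endline correlation appears in either document. The SAP has no sample size section.

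**The concern.** About 240 children per arm is a small sample for detecting 6 or 7 points on proportions near one half to two thirds, so power above 80% is surprising. A difference-in-differences analysis can gain precision from repeated measurement, but only if each child's status is highly stable between rounds. The quantity that decides this is the one left out.

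The protocol calls 6 and 7 points clinically relevant. If true power is well below 80%, effects of exactly that size would often be missed, and a reader relying on the stated power could take a non-significant result as evidence against them.

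**Working it through.** **Inputs.** From Protocol 1.5: 102 clusters of 5, ICC 0.02, attrition 5% or 10%, two-sided 0.05, anemia 66% with a 6-point difference, MAD 46.8% with a 7-point difference. From 1.3: 1:1 allocation, so 51 clusters per arm.

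**Effective sample size at 5% attrition.** Children per cluster: 5 × 0.95 = 4.75. Per arm: 51 × 4.75 = 242.25. Design effect: 1 + 3.75 × 0.02 = 1.075. Effective n: 242.25 / 1.075 = 225.3 per arm. At 10% attrition it is 229.5 / 1.07 = 214.5.

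**Endline comparison.** Power = Φ(δ/SE − 1.96) + Φ(−δ/SE − 1.96).

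- Anemia, 66% v 60%: SE = √[(0.66×0.34 + 0.60×0.40)/225.3] = 0.0454, δ/SE = 1.32, power 26.2% (25.2% at 10% attrition).
- MAD, 46.8% v 53.8%: SE = 0.0470, δ/SE = 1.49, power 31.9% (30.7%).

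**Attempts to reproduce the stated 81.7% / 88.8%.** Other endline conventions give, for anemia / MAD: one-sided test 37% / 44%; no clustering 28% / 34%; 104 villages 26.5% / 32.3%; 102 clusters in each arm 46% / 56%; the last with both rounds also counted as independent observations 75% / 84%. Adjusting for baseline (ANCOVA) reaches the stated values only at a correlation of about 0.88 to 0.89. None of these delivers both figures from the listed inputs.

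**Planned difference-in-differences.** With within-child correlation ρ, and assuming the same design effect applies to change, variance = 2(1 − ρ) × endline variance. The values of ρ below are assumptions. The detectable difference is (1.96 + 0.84) × SE.

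| ρ | Anemia / MAD power, 5% attrition | Same, 10% attrition | Detectable at 80% power, 5% attrition (points) |
|---|---|---|---|
| 0.3 | 20.1% / 24.2% | 19.3% / 23.3% | about 15 |
| 0.5 | 26.2% / 31.9% | 25.2% / 30.7% | about 13 |
| 0.7 | 40.0% / 48.5% | 38.4% / 46.7% | about 10 |
| 0.8 | 55.2% / 65.4% | 53.1% / 63.2% | about 8 |
| 0.85 | 67.5% / 77.6% | 65.3% / 75.6% | about 7 |
| 0.89 | 80.5% / 88.8% | 78.5% / 87.3% | about 6 |
| Stated | 81.7% / 88.8% | 80% / 87.3% | 6 / 7 are the targets |

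At 5% attrition, power reaches 50% at ρ = 0.773 (anemia) and 0.711 (MAD). Setting the ICC to 0 adds only 1 to 3 points for ρ up to 0.85, so the ICC is not what drives the result.

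**Solving back from the stated power.** The implied SE for anemia at 5% attrition is 0.06/(0.904 + 1.96) = 0.02095. With the baseline variance in all four cells, 1 − ρ = 0.02095² × 225.3 / (4 × 0.2244) = 0.110, so ρ = 0.890. The other three stated figures also give 0.890. With the variances used in the table, the answers are 0.894 for anemia and 0.890 for MAD.

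**What 0.89 would mean.** If control prevalence is flat, the share of control children changing status is 2p(1 − p)(1 − ρ). That is 2 × 0.2244 × 0.11 = 4.9% for anemia and 2 × 0.2490 × 0.11 = 5.5% for MAD, or about 12 and 13 of 242 children. Baseline is in May/June and "the endline data collection will take place in October 2022". MAD rests on one day: "A 24-hour open dietary recall will be conducted with mothers to assess their child's dietary intake over the previous day". Its meal-frequency threshold also changes with age for breastfed children: "2x/day for breastfed infants 6-8.9 months; 3x/day for breastfed children 9-23.9 months".

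**The pilot.** The survey was cross-sectional, so the pilot is the only repeat measurement reported. Section 1.4 says the team "conducted a pre- and post-intervention pilot study to examine its feasibility and potential for impact", and 1.5 adds: "Our pilot study found a 19.2% increase in MAD". If that is an absolute rise in the same children, the largest possible correlation is √[p(1 − p′)/(p′(1 − p))] with p′ = p + 0.192. This peaks at 0.404/0.596 = 0.678. If the rise is relative, 46.8% to 55.8% gives 0.835 and 39.3% to 46.8% gives 0.857. On these readings the pilot does not supply 0.89 for MAD.

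**The case against.** The strongest reply is that the stated powers fit one omitted value, so this is an undisclosed assumption rather than a miscalculation, and that endline-only figures describe an analysis the trial does not plan. The first part is probably right, and the planned model is the fair test. It is applied above, and it reaches the stated power only at about 0.89.

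The match is also weaker than four agreeing figures suggest. The two attrition cases are not independent, and exact agreement for anemia depends on the variance convention. Anything that multiplied the information by about 4.5 would fit as well. That stands, but changing the convention moves the required value only from 0.890 to 0.894.

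The pilot argument carries little weight. Section 1.4 also describes the gain as relative to a control group and then says there was none, so the meaning of 19.2% is unclear. A 4-week uncontrolled pilot with 47 triads does not bound the trial's correlation in any case. Similarly, with flat control prevalence 0.89 slightly exceeds the maximum possible in the intervention arm (0.879 anemia, 0.869 MAD), but it becomes feasible if the control arm worsens by 3 points. Neither remark sets a ceiling on power. The meal-frequency step affects only breastfed children who pass 9 months between visits.

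Stratification and covariate adjustment are left out of the calculation. They are unlikely to close a gap of this size. Finally, data collection was scheduled to end in 2022, so restating power changes no estimate; it does change how a null result may be read.

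**Conclusion.** The concern holds. The inputs listed in Protocol 1.5 do not deliver the stated power. For the planned difference-in-differences, power at 5% attrition ranges from about 20% to 68% (anemia) and 24% to 78% (MAD) as the assumed correlation goes from 0.3 to 0.85. Only about 0.89 gives the stated figures, and neither document states or justifies it. Below about 0.77 (anemia) or 0.71 (MAD), the trial is more likely than not to miss a true effect of the target size.

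This rests on the normal approximation and on applying the stated design effect to change. The true correlation is unknown, so 0.89 is not shown to be impossible. The shortfall is specific to the 6- and 7-point targets: a MAD difference of 19.2 points (46.8% v 66.0%) would have at least 94% power at a correlation of 0.3 or more.

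**What to change.** In Protocol 1.5 and 4.3 C, replace the power statements with figures for the two-arm difference-in-differences model. Give the formula and the within-child correlation with its source, or show power over a range such as 0.3 to 0.9. State the difference detectable at 80% power: about 15 to 10 points for correlations of 0.3 to 0.7, about 8 at 0.8, and about 13 for an endline comparison. Qualify the claim of adequate power in 4.3 C to match. Add one sentence saying that a non-significant primary result will be interpreted from its confidence interval against the 6- and 7-point targets.

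The cost is wording in two sections plus that sentence, with no extra data or enrolment. If 0.89 has a source, citing it settles the matter. If it has none, the stated power becomes a range that is less favourable over most of its span.

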1.6 Study Variables

A. Independent Variables, Interventions, or Predictor Variables

An mHealth messaging intervention will be delivered to the intervention group for this study, as described above. The intervention will be 16 weeks in duration and include both scripted and unscripted messages related to 8 key IYCF behaviors.

B. Dependent Variables or Outcome Measures

Table 1 provides an overview of our primary and secondary study outcomes.

Table 1. Study outcomes

Outcome type	Outcome	Description
Primary	Anemia prevalence	We will use Hemocue Hb301 machines to measure hemoglobin levels in children in order to determine anemia prevalence using the WHO cut-offs: mild $10 \leq \text{hb} < 11 \text{ g/dl}$; moderate $7 \leq \text{hb} < 10 \text{ g/dl}$ and severe $\text{hb} < 7 \text{ g/dl}$. A finger prick will be used to obtain a drop of capillary blood that is placed on a cuvette and inserted in the Hemocue machine to obtain an on-the-spot assessment of hemoglobin levels.
	Minimum Acceptable Diet	Minimum Acceptable Diet Prevalence, Primary, baseline and endline: The minimum acceptable diet indicator will be used to assess dietary diversity in children. A 24-hour open dietary recall will be conducted with mothers to assess their child's dietary intake over the previous day. The 24-hour recall will be used to calculate minimum dietary diversity (MDD) (consuming ≥ 4 of 7 food groups (grains, roots and tubers; legumes and nuts; dairy products; flesh foods; eggs; vitamin A rich fruits and vegetables; other fruit and vegetables)) and minimum meal frequency (MMF) (2x/day for breastfed infants 6-8.9 months; 3x/day for breastfed children 9-23.9 months; 4x/day for non-breastfed children 6-23.9 months). Children who meet the thresholds for both MDD and MMF are defined as consuming a MAD, based on the WHO/UNICEF IYCF indicator.

Secondary	Frequency of consuming key foods in past 7 days	Frequency of consuming key foods in the past 7 days, Secondary, baseline and endline: We will use a 7-day food frequency questionnaire (FFQ) to assess the frequency that children consumed specific foods targeted in the intervention over the course of the previous week. More specifically, the FFQ will ascertain the number of times that the following foods have been consumed: eggs, leafy greens, fish, milk, cowpea, nuts, orange colored fruits and vegetables, other fruits and vegetables, thick porridge, beef or mutton, pork, chicken and liver.
	IYCF practices	IYCF practice indicators, secondary, baseline and endline: We will use the WHO/UNICEF IYCF indicators to assess feeding practices. Mothers will be asked about feeding practices as part of the household surveys. These include: Bottle feeding 0–23 months; Continued breastfeeding 12–23 months; Exclusive breastfeeding under six months; Exclusively breastfed for the first two days after birth; Egg and/or flesh food consumption 6–23 months; Early initiation of breastfeeding; Ever breastfed; Introduction of solid, semi-solid or soft foods 6–8 months; Minimum dietary diversity 6–23 months; Mixed milk feeding under six months; Minimum meal frequency 6–23 months; Minimum milk feeding frequency for non-breastfed children 6–23 months; Sweet beverage consumption 6–23 months; Unhealthy food consumption 6–23 months; Zero vegetable or fruit consumption 6–23 months The proportion of children being fed according to the detailed descriptions of these indicators will be assessed based on the WHO/UNICEF IYCF indicator manual.
	IYCF knowledge, attitudes, norms and intentions	IYCF knowledge, attitudes, norms and intentions, Secondary, baseline and endline: IYCF knowledge, attitudes, norms and intentions will be assessed using survey questions based on the components of the intervention. Both mothers and fathers will be asked the survey questions as part of the household survey. The questions are grounded in the theory of planned behavior and based on previously published IYCF knowledge, attitudes, norms and intentions questions by Monterrosa et al. ¹ The questions have been pilot tested by the project PI.

1.7 Drugs/Devices/Biologics

A. Schedule and Administration

Not applicable.

B. Drug/Device Accountability and Storage Methods

Not applicable.

1.8 Specimen Collection

A. Primary Specimen Collection

We will use Hemocue machines to assess hemoglobin levels; however, this does not involve specimen collection. It simply involves a few drops of blood which are placed on a cuvette and discarded directly after analyzing it within the Hemocue machine.

- **Types of Specimens**: Not applicable.
- **Annotation**: Not applicable.
- **Transport**: Not applicable.
- **Processing**: Not applicable.
- **Storage**: Not applicable.
- **Disposition**: Not applicable.

B. Secondary Specimen Collection

Not applicable.

1.9 Data Collection

A. Primary Data Collection

- **Location**: We will conduct cognitive testing of messages as well as household surveys (including hemoglobin measurements of infants and young children) outside of the homes of survey participants. In the local context of this study, households generally have a small dwelling and a surrounding yard/compound. Based on our team's previous experience working with these communities in Senegal, there is a preference for conducting surveys outside the home in the surrounding yard. This allows sufficient space while also allowing for privacy during the interviews.
- **Process of Data Collection**: We will work closely with a team of local enumerators from Senegal. We have previously worked with these enumerators in Senegal and they have extensive knowledge of the communities in which this study will take place. In addition to their previous experience working with these communities, the enumerators will be trained by the PI, supported by our local partners (Institut de Recherche en Santé de Surveillance Epidemiologique et de Formation) in Senegal; IRESSEF), to assist with data collection. Our local partners have experience working with the local enumerators and conducting similar work in these communities. The enumerators are not part of the research team but will be paid for their services, which is typical of research conducted in these settings.
- **Timing and Frequency**:

Cognitive testing: Participants included in the cognitive testing will only have one visit (~30-45 minutes) with the study team.

cRCT and process evaluation: Each participating household will have two visits from the study team. One visit for the baseline data collection and a second for the endline data collection. In addition, participants who will take part in the semi-structured interviews as part of the process evaluation, will have third study visits by our team.

In addition to the study visits to collect data, participants will receive voice and text messages to their cellular phones one time per week. Each message will be approximately 2 minutes in duration. The messages will continue for a period of sixteen weeks (total of 16 messages).

After the completion of the message two automated questions will be asked, including: Did you understand the message?; Did you find the message useful? Do you intend to adopt this behavior? The response to the message will be keyed into the phone (1= yes; 2=no). In the event that a participant states that they did not understand the message, we will make note of it and then follow-up with them at the time of the post-intervention survey. There will also be an option to call a local number to gain additional information. The OuA Platform being used in this study will track whether the call was answered, how long it was listened to and the answers to the questions relating to message understanding, usefulness and intention to adopt the behavior.

Food environment data: The collection of food environment data will coincide with the baseline and endline food environment measures.

- **Procedures for Audio/Visual Recording:**

Cognitive testing: The cognitive testing will only involve taking detailed notes of the interviews with participants. We will not audio-record the interviews.

Process evaluation: The process evaluation conducted alongside our cRCT will involve audio-recording interviews. We will use a recording device to record the interviews. However, if participants do not wish to be audio-recorded, we will instead take detailed notes. Consenting to being audio-recorded is not a requirement of participating in the process evaluation component of the study.

Only members of the study team will have access to the audio-recordings. After each interview has been completed, we will download the recording onto the PI's password protected computer and erase it from the recording device. The only identifiers that the recording will include is the participants' voice.

- **Study Instruments:**

rRCT survey instrument: We have included the survey instrument in this IRB application. The questions used in this survey include those from the WHO/UNICEF indicators, questions from the Senegalese Demographic Health Survey, the Food and Agriculture Organization Food Insecurity Experience Scale as well as questions related to knowledge, attitudes and behavior that we have already used in our pilot

study in Senegal. In addition, we will also complete a short village survey with each of the heads of the farming groups at baseline. This will help to provide us with information that will inform our analyses.

Food environment data: We have included the food environment assessments with our protocol.

▪ **Ethnographic Studies, Interviews, Or Observation:**

Cognitive testing: During the cognitive testing, we will ask participants the following questions for each of the IYCF messages:

1. Why did you answer that way?
2. What does the question mean to you?
3. Can you repeat the question in your own words?
4. How would you word it differently to make it easier for other respondents to answer?

Process evaluation: We have include the interview guide for the process evaluation as an attachment with our IRB application. The questions are guided by a previously published process evaluation framework.³³

▪ **Subject Identifiers:**

Cognitive testing and process evaluation: We will not collect identifiers (with the exception of voice recordings for the process evaluation) as part of the cognitive testing and process evaluation.

[figure not shown]
cRCT: We will collect identifiers (names, telephone numbers and GIS coordinates of household) for the cRCT and these will be retained only until the study activities are completed. Individuals will be assigned personal identification numbers in order to protect their identity. All electronic and hardcopy documents will refer only to the identification numbers and the names of the subjects will not be linked to their data once it has been downloaded from the survey platform.

B. Secondary Data Collection

Not applicable. We do not plan to use secondary data.

